5. TREATMENT/INTERVENTION PLAN

This is a phase II, single arm, multi-center trial that will evaluate the combination of olaparib 300mg twice daily (600mg total daily dose) with durvalumab 1500mg IV monthly in biochemically recurrent castration sensitive prostate cancer. The trial will be conducted at sites who are members of the PCCTC Network.

As seen in the trial design (Figure 2), subjects will be treated concurrently with olaparib + durvalumab continuously for 24 months. After the first 4 months, if a subject fails to achieve an undetectable PSA with the combination of olaparib and durvalumab, ADT will be added for 6 months (starting at Cycle 5) while continuing treatment with olaparib and durvalumab. For subjects who have an undetectable PSA [PSA of <0.05 or PSA <0.10] for institutions where this is the lower limit of detection] after the first 4 months of treatment, they will continue on the combination of olaparib + durvalumab continuously for 24 months (without ADT). As long as it is believed that subjects are clinically benefiting, they will remain on treatment for up to 24 months with olaparib and durvalumab. For example, a subject with a PSA reduction that does not achieve an undetectable PSA would be allowed to remain on study for the duration of the trial. Subjects who meet progression criteria while on active therapy would come off of trial. If subjects respond and later progress in the one-year follow-up period (beyond 24 months), they will be allowed to be re-induced with the combination.

Figure 2. Study schema for olaparib and durvalumab in subjects with castration-sensitive prostate cancer (biochemical recurrence) harboring DNA damage repair mutations

DDR deleterious mutations (somatic or germline) will include BRCA1 (breast cancer susceptibility gene), BRCA2, ATM (ataxia telangiectasia mutated serine/threonine kinase), CHEK2, FANCA, RAD51C, RAD51D, PALB2, BRIP1, BARD1, and CDK12. Mutations may be truncating, splice site mutations, missense or homozygous deletions. Subjects will be allowed on trial using local testing, previously obtained genomic testing from a validated lab (e.g., expedited germline testing from Color), or via archival or fresh tissue.

The following assessments and procedures will occur during the study. A schedule of assessments is provided in Appendix B.

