In the event of a \leq Grade 2 infusion-related reaction, the infusion rate of study drug may be decreased by 50% or interrupted until resolution of the event (up to 4 hours) and re-initiated at 50% of the initial rate until completion of the infusion. For subjects with a \leq Grade 2 infusion-related reaction, subsequent infusions may be administered at 50% of the initial rate. Acetaminophen and/or an antihistamine (e.g., diphenhydramine) or equivalent medications per institutional standard may be administered at the discretion of the investigator. If the infusion-related reaction is Grade 3 or higher in severity, study drug will be discontinued. The standard infusion time is one hour; however if there are interruptions during infusion, the total allowed time from infusion start to completion of infusion should not exceed 8 hours at room temperature, with maximum total time at room temperature not exceeding 8 hours (otherwise requires new infusion preparation). For management of subjects who experience an infusion reaction, please refer to the toxicity and management guidelines in Appendix G.

As with any antibody, allergic reactions to dose administration are possible. Appropriate drugs and medical equipment to treat acute anaphylactic reactions must be immediately available, and study personnel must be trained to recognize and treat anaphylaxis. The study site must have immediate access to emergency resuscitation teams and equipment in addition to the ability to admit subjects to an intensive care unit if necessary.

Supply and packaging

Durvalumab (MEDI4736) will be supplied in glass vials containing 500 mg of liquid solution at a concentration of 50 mg/mL for intravenous (IV) administration.

Durvalumab (MEDI4736) will be supplied by AstraZeneca as a 500-mg vial solution for infusion after dilution. The solution contains 50 mg/mL durvalumab (MEDI4736), 26 mM histidine/histidine-hydrochloride, 275 mM trehalose dihydrate, and 0.02% (weight/volume) polysorbate 80; it has a pH of 6.0. The nominal fill volume is 10 mL.

Storage requirements

All study drugs should be kept in a secure place under appropriate storage conditions. Drug product should be kept in original secondary packaging until use to prevent prolonged exposure

to light. The investigational product label on the bottle and the Investigator Brochure specifies the appropriate storage.

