10. STATISTICAL CONSIDERATIONS

10.1 Study Endpoints

10.1.1 *Primary endpoint*

Undetectable PSA with recovered testosterone (non-castrate defined as testosterone > 150ng/dL) at 24 months. Undetectable is defined as PSA < 0.05 ng/ml. For institutions where the lower limit of detectable is 0.10 ng/ml, then undetectable will be defined as PSA <0.10 ng/ml.

10.1.3 *Secondary endpoints*

- Undetectable PSA at 5 months (with the combination of durvalumab and olaparib, no ADT)
- Safety of the combination of durvalumab and olaparib will be determined by the summary of AEs

10.1.4 *Exploratory endpoints/correlative studies*

- Measurement of patient reported toxicities using PRO-CTCAE at screening, cycle 5, cycle 11, and EOT. Changes over time and comparison to clinician reported toxicities (CTCAE v5.0)
- Blood biomarkers at cycle 1, cycle 2, cycle 5, cycle 11, and end of treatment: PBMCs collected to assess immunomodulation, for example, changes in T -cell populations over time, multiplex cytokine analysis, tumor associated antigens; cfDNA will also be collected at cycle 1, cycle 5 and end of treatment for potential future use.
- Archival tissue for analysis of immune activating genes and PDL1 expression
- Undetectable PSA at 11 months (irrespective of testosterone level)
- PSA PFS
- Change in PSA doubling time relative to trial entry

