10.3.2 Safety population

All subjects enrolled in the study who receive at least one dose of study drugs will be included in the safety analysis population and considered evaluable for toxicity and safety from the time of their first dose.

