10.4 Safety Analysis

10.4.1 Evaluation of adverse events

Treatment-emergent adverse events will be summarized (number and percentage of subjects) for all subjects who receive at least one dose of both investigational therapies. Adverse event summaries will be organized by body system, frequency of occurrence, intensity (i.e., severity grade), and causality or attribution. Subjects who experience an adverse event more than once will be counted only once. The occurrence with the maximum severity will be used to calculate intensity.

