10.4.2 Evaluation of serious adverse events and premature withdrawals

Adverse events deemed serious and those resulting in treatment withdrawal or death will be summarized separately.

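### The adverse-event table in 10.4.1 is limited to men dosed with both drugs, which conflicts with the 10.3.2 safety population and can leave out a man who stops after reacting to whichever drug he takes first

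*Combined protocol and SAP*

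**What the plan says.** Section 10.3.2 defines the safety set: "All subjects enrolled in the study who receive at least one dose of study drugs will be included in the safety analysis population". It adds that these men are "considered evaluable for toxicity and safety from the time of their first dose".

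Section 10.4.1, which follows directly, gives numbers and percentages of subjects with treatment-emergent adverse events, but only "for all subjects who receive at least one dose of both investigational therapies".

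Section 10.1 makes this summary the basis of a secondary endpoint: "Safety of the combination of durvalumab and olaparib will be determined by the summary of AEs". Section 2.2 lists safety of the combination as a secondary objective.

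Section 10.4.2 adds a further summary: "Adverse events deemed serious and those resulting in treatment withdrawal or death will be summarized separately". It names no population.

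On dosing, section 5 says "subjects will be treated concurrently with olaparib + durvalumab continuously for 24 months". Section 6.2 sets no order for the two drugs on infusion days. Section 6.1 says of infusion reactions: "If the infusion-related reaction is Grade 3 or higher in severity, study drug will be discontinued".

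**The concern.** Receiving the second drug is something that happens after treatment starts, and it can depend on how a man tolerated the first. An analysis set that requires both drugs can therefore select on the outcome it is meant to report. A man removed from the table because of a reaction necessarily had that reaction, so for that event the loss can only lower the tabulated rate.

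The plan would also treat the same man in different ways. If eligible, he belongs to the efficacy set in 10.3.1 and could count as a failure under 10.2. He could count toward the stopping rule in 10.2, and his exposure is summarised under 10.4.4. Yet he would be missing from the adverse-event table. In a trial of 32 men, one or two such absences are visible in the percentages.

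**Working it through.** **1. The populations side by side**

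| Section | Use | Who is counted |
|---|---|---|
| 10.2 | Toxicity stopping rule | Subjects; no both-drugs condition |
| 10.3.1 | Efficacy | Eligible subjects with at least one dose of study drugs |
| 10.3.2 | Safety population | Enrolled subjects with at least one dose of study drugs, from first dose |
| 10.4.1 | Adverse-event table | Subjects with at least one dose of both drugs |
| 10.4.2 | Serious events; events causing withdrawal or death | Not stated |
| 10.4.4 | Exposure | All subjects |

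Only 10.4.1 requires both drugs.

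**2. How a man could be left out**

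He must stop permanently after one drug and before any dose of the other. Durvalumab is given on Day 1 of each cycle with a window of 3 days either side (section 6.1 and Appendix B), and olaparib is dispensed on Day 1 (section 6.2). The first doses can therefore be separated by hours or a few days, in either order. Section 6.1 stops study drug after a Grade 3 or higher infusion reaction; the infusion-reaction table in Appendix G refers to study drug/study regimen, so it is not clear whether one drug or both is meant. Sections 5.4 and 6.5 allow continuation on the other agent. The route exists but is narrow.

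**3. The plan's own figures**

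- Stopping rule (4 in 8, 5 in 16, 7 in 24, 9 in 32), by exact sequential binomial calculation: crossing probability 0.1123 at a true rate of 0.15 (stated 0.11) and 0.8922 at 0.35 (stated 0.89). Both reproduce.
- Efficacy rule, 8 or more of 32: exact size 0.0958 at 0.15 (stated 0.10) and power 0.918 at 0.35 (stated above 0.90). Both are consistent.

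Neither depends on the adverse-event table, so neither changes under the fix.

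**4. Effect on a tabulated rate**

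Let x be the number of men with a given event among 32 dosed, and k the number of those x who received only one drug. The documents give neither, so both are assumptions.

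- Safety population: x/32
- Both-drugs table: (x − k)/(32 − k)

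| x | k = 0 | k = 1 | k = 2 |
|---|---|---|---|
| 4 | 4/32 = 12.5% | 3/31 = 9.7% | 2/30 = 6.7% |
| 6 | 6/32 = 18.8% | 5/31 = 16.1% | 4/30 = 13.3% |
| 8 | 8/32 = 25.0% | 7/31 = 22.6% | 6/30 = 20.0% |

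Each affected man lost lowers the rate by about 2 to 3 percentage points. With k = 0 there is no difference.

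**The case against.** The strongest reply has four parts.

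- **The plural.** Study drugs in 10.3.2 could mean the two-drug regimen, and the objective concerns the combination, so a both-drugs table might be intended. This is possible, but evaluability from the first dose fits the any-dose reading better. If both drugs were meant, 10.3.2 would itself need rewording. Either way the text has to change.
- **The mechanism is thin.** There is no olaparib lead-in, dosing is concurrent, and a man who stops one drug may continue on the other. Any dose of the second drug puts him in the table. This stands, and it limits the number affected to few or none.
- **Other summaries may catch him.** Section 10.4.2 has no both-drugs condition, and a severe reaction that ends treatment is the kind of event it covers. This stands in part: because its population is unstated, a reader cannot be sure that it repairs the gap, and it does not restore the 10.4.1 percentages.
- **No decision changes.** The stopping rule is not restricted to men given both drugs, and the efficacy rule is unaffected. This stands in full.

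A reader might infer more: that the men with the earliest severe toxicity vanish from all the trial's toxicity rates, or that the exclusion could bring an observed rate below the 15% in section 10.2. The documents support neither. The loss is shown only for the 10.4.1 table. The 15% is one of two true rates at which the stopping boundary is evaluated, and section 10.2 does not label it acceptable. It also refers to a specific composite: Grade 3 or greater immune toxicity needing steroids, or Grade 3 or greater non-immune toxicity needing discontinuation. The illustrative counts are for any given event, so no comparison with 15% is warranted.

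**Conclusion.** The point holds for the 10.4.1 table. Its population conflicts with the natural reading of the safety population in 10.3.2, depends on what happens after dosing starts, and is not reconciled anywhere. For an event that causes a man to stop before the other drug, the possible bias in its tabulated rate is downward.

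The expected size is small. It is nil if every man receives both drugs. On assumed counts of 4 to 8 events in 32 men, it is about 2 to 3 percentage points for each affected man lost. The conclusion rests on reading 10.3.2 as any dose of either drug, and on at least one man stopping in the short interval between first doses. It does not extend to the stopping rule or the efficacy analysis. The change is still worth making, because the table supports a named secondary endpoint and the correction is simple.

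**What to change.** - In 10.4.1, summarise treatment-emergent adverse events in the 10.3.2 safety population.
- Word that population identically in 10.3.2 and 10.4.1, as at least one dose of either olaparib or durvalumab.
- State that 10.4.2 uses the same population.
- List any subject who received only one drug, with the drug received and the reason the other was not given.
- If a view of men exposed to the combination is wanted, keep the both-drugs table and label it supplementary.

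The cost is a few sentences in section 10. Adverse events are already recorded from consent (sections 7.1.1 and 7.3.1), so no new data are needed. The sample size, efficacy rule and stopping probabilities stay as they are. Separately, section 6.1, the infusion-reaction table in Appendix G, and sections 5.4 and 6.5 should be reconciled on whether stopping after an infusion reaction concerns one drug or both; that is for the clinical team to settle.

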10.4.2 Evaluation of serious adverse events and premature withdrawals

Adverse events deemed serious and those resulting in treatment withdrawal or death will be summarized separately.

10.4.3 Evaluation of laboratory parameters and assays

Selected clinical laboratory parameters will be summarized and clinically significant changes from baseline will be discussed.

10.4.4 Extent of exposure

Treatment exposure will be summarized for all subjects, including dose administration, number of cycles, dose modifications or delays, and duration of therapy.

10.5 Statistical Procedures and Analysis

Summary statistics include the number of observations, mean, standard deviation, median, minimum, and maximum values.

Statistical methods for the analyses

An exact binomial test will be used to evaluate the efficacy of the 24 months undetectable PSA endpoint. In addition, the proportion of subjects that attain an undetectable PSA at (1) 5 months, (2) 11 months, and (3) 24 months will be computed along with their attendant 95% confidence intervals. The probability of PSA progression over time will be estimated using the cumulative incidence function.

A paired t-test will be used to compare the PSA doubling time at 24 months to the PSA doubling time at study entry.

Kendall's tau with longitudinal data will be used to compare patient recorded toxicities to physician recorded toxicities over time.

The immunologic profile of patients over time will be described using nonparametric kernel smoothing.

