2.3 Exploratory Objectives

To determine:

- Undetectable PSA at 11 months (cycle 11) (irrespective of testosterone level)
- Time to PSA progression defined as the time to PSA increase that is $\geq 25\%$ and $\geq 2\text{ng/mL}$ above the nadir, and which is confirmed by a second value > 3 weeks later
- Change in PSA doubling time at 24 months relative to PSA doubling time from the first dose of study drug (using the last 3 values from each time point)
- Comparison of Patient Reported Outcome (PRO) assessments of toxicity (PRO-CTCAE) to clinician reported toxicity assessments (CTCAE v.5.0)
- Changes in immune biomarkers with treatment. Peripheral blood mononuclear cells (PBMCs) will be collected that can later be analyzed for the immunomodulatory effects of the regimen by measuring for example, discrete T-cell populations. Archival tissue will also be analyzed for immune-related genes that may associate with response.

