3.1.2 Males 18 years of age and above

3.1.3 Body weight $> 30\text{kg}$

3.1.4 History of radical prostatectomy and/or primary radiation therapy to the prostate

3.1.5 Histologically confirmed prostate cancer with progressive disease defined as:

- Rising PSA (50% or more increase to a level of 0.50 ng/mL or more, based on at least 3 PSA determinations obtained at least 1 week apart). The 50% rise in PSA is across the 3 determinations, and these determinations do not need to be sequential.
- PSA doubling time of \leq 9months as calculated according to the Memorial Sloan Kettering Cancer Center nomogram
(<http://www.mskcc.org/mskcc/html/10088.cfm>)

3.1.6 No evidence of metastatic disease on conventional imaging (CT/MRI and bone scan). However, subjects with pelvic and/or retroperitoneal nodes $< 2\text{cm}$ in the short axis will be permitted on study, as they are considered not to have definitive metastases. (Note: *Metastatic disease on investigational imaging, Prostate Specific Membrane Antigen-targeted (PSMA) PET, PET-choline, or other novel PET tracers who do not have evidence of metastatic disease using conventional imaging (CT/MRI, bone scan) are allowed.*)

3.1.7 Molecular evidence of DDR deleterious mutations (somatic or germline), including BRCA1, BRCA2, ATM, CHEK1, CHEK2, FANCA, RAD51B, RAD51C, RAD51D, RAD54L, PALB2, BRIP1, BARD1, or CDK12. Mutations may be truncating, splice site mutations, missense or homozygous deletions. Mutation status is determined by a local laboratory with the result documented in the subject's medical record, previously obtained genomic testing from a CLIA-certified lab, or via archival or fresh tissue.

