8. CRITERIA FOR OUTCOME ASSESSMENT/THERAPEUTIC RESPONSE

8.1 Therapeutic Response

8.1.1 PSA

This trial will measure PSA monthly for the first 24 months. The primary endpoint is an undetectable PSA at 24 months with non-castrate levels of testosterone (>150 ng/dL).

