10.2 Sample Size Determination

The primary objective of the study is to determine the efficacy of the combination of olaparib with durvalumab in subjects with biochemically recurrent castration sensitive disease. The primary endpoint of the study is maintaining an undetectable PSA with recovered testosterone at 24 months and this event is defined as a success. Subjects that withdraw prior to the 24 month follow up time are deemed as failures for the primary endpoint. A single stage design that differentiates between population success rates of 0.15 and 0.35 will be used to assess treatment activity.⁶³

Thirty-two subjects will be accrued to this trial. If eight or more successes are observed, it is concluded that the therapy is sufficiently active to warrant further study. This design has power greater than 0.90 for a population success proportion of 0.35 using a one-sided test with size 0.10 for the population success rate 0.15.

In addition to the evaluation of the primary endpoint, the study will be monitored for unacceptable toxicity, which is defined as Grade 3 or greater immune related toxicity requiring steroids or \geq Grade 3 non-immune toxicity requiring trial discontinuation. The stopping rule for excessive toxicity and the corresponding power calculation is provided in the table below.

Toxicity	# of toxicities needed to stop the study	Toxicity rate in the population	Probability boundary is crossed
\geq Grade 3 immune related toxicity requiring steroids or \geq Grade 3 non-immune toxicity requiring trial discontinuation	4 in the first 8 subjects	0.15	0.11
	5 in the first 16 subjects 7 in the first 24 subjects 9 within 32 subjects	0.35	0.89

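### The exploratory paired t-test on raw PSA doubling time is ill-suited to undetectable, flat or falling PSA at month 24, and the plan gives no rule for those cases or for missing values

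*Combined protocol and SAP*

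**What the plan says.** All references are to the combined protocol and SAP.

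- **Method.** Section 10.5: "A paired t-test will be used to compare the PSA doubling time at 24 months to the PSA doubling time at study entry."
- **Data used.** Section 2.3 lists the comparison as an exploratory objective, "using the last 3 values from each time point". Section 10.1.4 lists it as an exploratory endpoint: "Change in PSA doubling time relative to trial entry".
- **Entry.** Inclusion criterion 3.1.5 requires a rising PSA, "based on at least 3 PSA determinations obtained at least 1 week apart", and a doubling time of at most "9months as calculated according to the Memorial Sloan Kettering Cancer Center nomogram". The nomogram is named for eligibility only. No formula is printed, and nothing says that the month-24 value comes from the same tool.
- **Sampling.** Section 8.1.1: "This trial will measure PSA monthly for the first 24 months." Appendix B defines a month as 28 days.
- **Who may be present at month 24.** Section 5 says that "a subject with a PSA reduction that does not achieve an undetectable PSA would be allowed to remain on study". It also takes subjects who progress on therapy off the trial.
- **Primary endpoint.** Success is an undetectable PSA with testosterone above 150 ng/dL at 24 months (section 10.1.1). Section 10.2: "If eight or more successes are observed, it is concluded that the therapy is sufficiently active to warrant further study." Early withdrawal counts as failure, but that rule is written for the primary endpoint only.

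No section says what to do in the doubling-time comparison when month-24 PSA is undetectable, flat, falling or missing.

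**The concern.** Doubling time is the reciprocal of a growth rate, up to a constant. It goes to infinity as growth slows to zero, changes sign when PSA falls, and cannot be computed from values reported only as below a limit. Eligibility makes every entry value finite and positive. The month-24 values need not be, because the state the trial hopes to produce, a durably undetectable PSA, is one in which a doubling time may not exist.

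Three things could go wrong within this endpoint. The test could run on a remainder that omits many of the best responders. Subjects whose PSA is falling could pull the mean change down, as a shortened doubling time would. And the choice between keeping and dropping such values would be made after the data are seen, with the answer depending on it.

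**Working it through.** **1. The plan's own figures.** The documents give no sample size, SD or power for this comparison. The primary rule reproduces: with n = 32 and at least 8 successes, the exact binomial size at 0.15 is 0.096 and the power at 0.35 is 0.918, consistent with the stated 0.10 and above 0.90.

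**2. Pairs at risk from undetectable PSA.** Expected successes are 32 × 0.15 = 4.8 and 32 × 0.35 = 11.2. If every success has all three last values below the reporting limit, the test keeps about 27 or 21 pairs at those rates, and at most 32 - 8 = 24 in a positive trial. None of the pairs kept is a success.

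**3. Flat or falling PSA.** The standard formula is assumed here: doubling time = ln2 / slope of ln(PSA). For three equally spaced values, the slope is [ln(third) - ln(first)] / (2 × spacing). The spacing is 28 days = 28/30.4375 = 0.920 calendar months.

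| Last three PSA values | Slope per month | Doubling time (calendar months) |
|---|---|---|
| 1.00, 1.00, 1.01 | 0.00541 | +128 |
| 1.00, 1.00, 0.99 | -0.00546 | -127 |
| 1.00, 0.95, 0.90 | -0.0573 | -12.1 |

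In the first two rows, a change of 2% in one value moves the result by about 255 months.

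**4. Effect on the mean (assumed fractions).** Take 16 evaluable pairs, all with an entry doubling time of 6 months. Some slow to 18 months (change +12). The rest fall as in the third row (change -12.104 - 6 = -18.104).

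| Falling | Mean change in doubling time (months) | Mean change in log-PSA slope (per month) |
|---|---|---|
| 0 of 16 | +12.0 | -0.077 |
| 4 of 16 | (12 × 12 - 4 × 18.104)/16 = +4.5 | -0.101 |
| 8 of 16 | (8 × 12 - 8 × 18.104)/16 = -3.1 | -0.125 |

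The mean turns negative once the falling fraction exceeds 12/(12 + 18.104) = 0.40. The slope orders the three cases correctly: each slowing pair contributes ln2/18 - ln2/6 = -0.077, and each falling pair -0.0573 - ln2/6 = -0.173.

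**5. Why a better test is not the whole answer.** Entry selects on an estimated doubling time of 9 months or less, so some entry estimates are short by chance. The simulation assumed 16 pairs with no true change, true doubling times lognormal (median 6 months, log-SD 0.3), and the qualifying values serving as the entry values. SE(slope) was sqrt(ln(1 + CV²)) / (√2 × spacing), and two-sided alpha was 0.05. A Wilcoxon signed-rank test on slope then shows significant lengthening in these shares of trials, against 2.5% nominal:

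| PSA CV | 2% | 5% | 10% | 20% |
|---|---|---|---|---|
| Entry values 2 months apart | 3% | 4% | 6% | about 10% |
| Entry values 28 days apart | 5% | 12% | 26% | 46% |

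Next, undetectable subjects were added at the best rank, with the other 16 unchanged and 2-month entry spacing. Over the same CV range the test is significant in about 36% to 61% of trials with 5 such subjects, and about 78% to 92% with 8.

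**The case against.** Four objections have force.

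- **A reader might infer that every subject undetectable at month 24 has no doubling time.** The documents do not support that. The threshold of 0.05 ng/mL (or 0.10 ng/mL at some sites) defines the endpoint and need not be where a laboratory stops reporting numbers. Section 1.2.8 itself cites a PSA nadir of 0.02. The pair is lost only when all three values are below the reporting limit. If only some are, the result depends on an unstated substituted value.
- **A reader might infer that the plan scores a falling PSA as a worsening.** That needs signed ln2/slope with negative values kept, and the documents print no formula. If the calculator returns nothing for a fall, there is no sign reversal. The subject then drops out because of the outcome, which is also not covered.
- **Section 5 is weak evidence of falling PSA at month 24.** It describes a reduced level, not a negative slope over the last three values, and any added ADT lasts 6 months from Cycle 5. The fractions in the worked example are invented.
- **The consequence is small.** No decision rule uses this endpoint. Section 10.5 separately reports undetectable proportions at 5, 11 and 24 months with confidence intervals, and its summary statistics include the number of observations, median, minimum and maximum, so lost pairs and extremes would be visible.

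These objections limit the size and certainty of the point. They do not supply the missing rule.

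**Conclusion.** The point holds as a minor one, confined to one exploratory endpoint. A paired t-test on raw doubling time does not fit outcomes that the trial expects. It can lose many of the successes, and it handles flat or falling PSA either erratically or by dropping subjects on outcome. The plan states neither the formula nor the handling.

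The loss of pairs rests on all three last values being below the reporting limit. The sign reversal rests on signed ln2/slope with negatives kept. The documents do not settle either, nor do they give the PSA CV, entry spacing (criterion 3.1.5 requires only one week), number of evaluable pairs or fraction falling. The numerical illustrations show direction and are not forecasts. The primary exact binomial test, the sample size and the 8-of-32 rule are untouched.

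**What to change.** Amend section 10.5 as follows.

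1. Replace the paired t-test with a descriptive analysis of the within-subject change in log-PSA slope (median and interval), among subjects with detectable values at both time points. State the formula and the time unit.
2. Show all 32 subjects in ordered month-24 categories:
   - undetectable with testosterone above 150 ng/dL;
   - undetectable with testosterone not recovered;
   - falling or flat;
   - rising more slowly than at entry;
   - rising as fast or faster;
   - no month-24 value (withdrawn or progressed), shown as its own category and not dropped.
3. Give doubling time only as a median, with subjects whose PSA is not rising labelled *not rising*.
4. Draw no confirmatory inference, because selection at entry leaves any before/after test open to regression to the mean.
5. Do not pool undetectable subjects as best-ranked in a signed-rank test. That would largely restate the primary endpoint and ignore its testosterone condition.

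The cost is a short amendment, with lead site/sponsor and PCCTC consent and IRB approval under section 11.2. No new data are needed: PSA is already measured monthly, and testosterone is already collected for the primary endpoint. The drawback is that slope is less familiar to clinical readers than doubling time.
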